^a Childbearing potential to be defined as women who are not yet post-menopausal who are not consistently utilizing an acceptable form of contraception. Acceptable forms of contraception to include hormonal methods such as oral contraceptives, patches, injections, vaginal ring, or implants, hormonal or copper intrauterine device, or history of surgical sterilization including tubal ligation or hysterectomy.

screening assessments will have the chance to review any questions with the study staff, as well as a recap of the follow-up schedule, and they will then receive their randomization assignment.

Recruitment efforts will be made by working with Mayo Clinic's Research Recruitment Services to develop marketing materials including a recruitment flyer in both print and digital formats, a social media recruitment plan leveraging Mayo Clinic's enterprise social media accounts for recruitment and other potential tactics to be determined after recruitment begins, directed towards the goal of boosting minority inclusion to be at least representative of the local population. Data will be pulled during the time of IRB submission and included to establish general targets justifying Exclusion #35 to help reserve spots for enrollment that are in-line with a representative population if they are not met by a certain threshold. At the time of this writing, Rochester, MN has demonstrated approximately 10% minority population.

Randomization

Participants will be randomly assigned to treatment or control group with a 1:1 allocation per a computer-generated randomization using variable block randomization.

Participants will be blinded to the results of randomization. They will remain blinded until the end of the study, or if there is medical or surgical safety concern. If any SAEs occur, subjects may be unblinded as defined by the Clavien-Dindo Grade III or above. Unblinding of subjects will be reported to IRB per local site IRB guidelines, if not meeting the criteria above. Measures will be taken to minimize or avoid bias in the study using "masking/blinding procedures." Randomization assignment will be recorded in the EDC and subject tracking, but will not be recorded within the EMR to reduce clinical team exposure to their randomized status for follow-up care. Research teams will not be blinded to the randomization results. Subjects will be asked to confirm with their study team if they have become aware of the procedure.

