All patients will undergo a standard moderate intensity life-style intervention administered over 12 visits in the first year after procedure. Participants will be required to follow up with their prescribing physician to make any necessary changes to their hypertension and/or type II diabetes medications at 3, 6, 9 and 12 months. Completion of patient follow-up with providers for medication adjustment will be captured with completion of the appropriate CRF at the corresponding visits. In the event that participants are unable to contact their physician or participants are experiencing symptoms related to the medication dosing requiring urgent action, the study team will make any necessary changes in their medication dosing and document these changes appropriately in the relevant CRFs. Any medication changes will be monitored and recorded by the study team. Laboratory testing will be obtained as detailed in the study schedule of events

Participants will return for follow-up visits per the schedule of events below. For all visits with the exception of weeks 1 and 4, an in-window visit will be considered as reporting for follow-up visits within a two-week window of the visit date.

At the time of the 6-month visit, each subject's 6-month de-identified EGD video will be shared with an external center for an additional blinded assessment of the primary endpoint (suture durability) by a qualified endoscopist. Each video will be classified objectively according to the aspect of the gastric tissue and the sutures (intact, partially intact, or open). This sharing will take place through Mayo SimpleShare system.

Schedule of Events (SOE)

Study Activity	Screening & Enroll.	Rand.	Procedure	Post-Op Call	Week 1	Week 4	Week 8	Week 12	Weeks 16, 20	Week 26 (Month 6)	Weeks 30, 36, 42, 48	Week 52 (Year 1)	Unscheduled Visit
Visit Number	-2	-1	0	1	2	3	4	5	6,7	8	9,10,11,12	13	
In-Window Day Range	45 to Rand.	60 to Proc.	00		+/- 2	+/- 3				+/- 14			
Informed Consent Form (ICF)	X												
Complete Physical Exam (CPE)*	X											X	X
Focused Physical Exam *					X								
EKG	X												
Formal nutritional assessment	X												
Formal psychology evaluation	X												
Pregnancy test **	X												
Laboratory tests ⁺	X										X		X
H-Pylori breath test (baseline only)													
Questionnaires ++	X							X		X		X	
Inclusion/Exclusion	X												
Procedure Assessment Form			X										
GERD Questionnaire & Activity Assessment Form	X				X	X	X	X	X	X	X	X	X

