8.2.1 Primary Aim

The primary outcomes are durability of plications and endoscopic sutures on repeat endoscopy at 6 months, in the two randomized arms.

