8.2.3 Secondary Analyses

A per-protocol analysis will compare randomized groups among protocol adherent patients – here, defined among as those actually receiving the procedure and making $\geq 80\%$ follow-up visit in both groups. Modified ITT will be considered the primary approach for all efficacy analyses and will include patients who actually received the intervention regardless of adherence to follow-up visits. Safety endpoints and adverse events may be evaluated based on treated group (per-protocol).

Additional outcomes and analyses not specified here are considered exploratory and post-hoc and will be clearly identified as such in any publications.

^b %TBWL defined as $[(\text{pre-operative weight} - \text{post-operative weight}) / (\text{pre-operative weight})] \times 100$

^c % EWL defined as $[(\text{pre-op weight} - \text{follow up weight}) / (\text{pre-op weight} - \text{ideal body weight})] \times 100$

Note: "Ideal body weight" of BMI 25

Missing Data

The primary analysis uses a hierarchical regression model, assuming post-randomization dropout is missing at random (MAR) among subjects completing at least 1 of the planned follow up visits.

Patients excluded after randomization and before intervention on the basis of identified exclusion criteria will be excluded from analyses; reasons for meeting exclusion criteria will be documented. Patients that withdraw/dropout between randomization and intervention are assumed to be missing completely at random. However, a sensitivity analysis will compare withdrawn subjects to participating subjects and perform analyses under MAR (including multiple imputation) assumptions if these subjects appear different or if dropout occurs at substantially different rate in one arm compared to the other. Participating patients who dropout prior to the first follow up visit will be analyzed similarly.

Randomization and Data Collection

Stratified block randomization schedules will be uploaded to REDCap. Data will be collected in REDCap data collection forms.

Interim Analysis

No interim analysis will be performed for efficacy endpoints. Adverse events will be monitored throughout and discussed with the data monitoring committee.

ETHICAL CONSIDERATIONS

This study is to be conducted according to United States government regulations and Institutional research policies and procedures.

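### The power assurance has no calculation behind it, and the week-26 durability endpoint has no designated lead read, no specified model and no rule for a missing endoscopy

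*Combined protocol and SAP*

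**What the plan says.** **Power.** *Replacement of withdrawn subjects* tells the reader that the sample size calculation has enough patients to give power after some dropout. *Power and Sample Size* fixes 12 per arm and says that, for a pilot, a formal power calculation is neither possible nor needed. The same section lists %TBWL as a further primary endpoint for sample size; *Endpoints Effectiveness* and 8.2.2 treat it as secondary.

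**Endpoint and readers.** Section 8.2.1 consists of one sentence: "The primary outcomes are durability of plications and endoscopic sutures on repeat endoscopy at 6 months, in the two randomized arms". The grade comes from one repeat EGD at 26 weeks +/- 2 weeks. *Trial Intervention* sends the video to an outside center for an "additional blinded assessment of the primary endpoint (suture durability) by a qualified endoscopist", and continues: "Each video will be classified objectively according to the aspect of the gastric tissue and the sutures (intact, partially intact, or open". The Schedule of Events and the Week 26 visit list call this step inter-observation. *Randomization* says "Research teams will not be blinded to the randomization results", but keeps assignment out of the medical record; the Week 26 list has the EGD done clinically.

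**Model and missing data.** *Missing Data* states: "The primary analysis uses a hierarchical regression model, assuming post-randomization dropout is missing at random (MAR) among subjects completing at least 1" of the planned visits. Conditional multiple imputation is offered for patients lost between randomization and intervention, and "Participating patients who dropout prior to the first follow up visit will be analyzed similarly". Under 8.2.3 the mITT set "will include patients who actually received the intervention regardless of adherence to follow-up visits".

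**Covariates.** Section 8.2.2 adjusts the ANCOVA of continuous secondary outcomes for the variables named in the primary analysis. None are named anywhere.

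**The concern.** The two power statements cannot both stand, and a reader who meets only the first will believe that the trial was sized to detect an effect.

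For durability, three decisions that can move the result are open: whose grade counts, how the three classes are compared, and what happens to a treated patient without a week-26 EGD. An MAR argument based on having at least one follow-up visit suits an outcome measured repeatedly. Here weight is repeated, but durability is graded once. With 12 per arm each patient is about 8% of an arm (1/12 = 8.3%), so one missing grade carries weight. The blinded external read is already paid for in effort, yet the plan appears to give it a secondary role.

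**Working it through.** **1. Power.** There is no figure to reproduce. The documents give N = 24 but no alpha, effect size, durability rates, SD or dropout rate, so the claim of sufficient power cannot be checked against anything.

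**2. Who has a durability grade.** Setting the rules side by side:

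| Patient | Covered by | Durability grade? |
|---|---|---|
| Lost before intervention | Assumed MCAR; conditional multiple imputation | No |
| Treated, lost before first visit | Handled in the same way | No |
| Treated, at least one visit, no week-26 EGD | MAR model sentence only | No |
| Treated, week-26 EGD readable | MAR model sentence | Yes |

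The third row is the gap. Whether the model's levels are visits, sutures or readers, this patient supplies no durability record. A likelihood-based model recovers something only if it jointly models other data, such as weight, and the plan does not say that it does.

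**3. Size of the missing-EGD problem.** All inputs are assumed, because the documents give none:
- two-sided 5% test; exact Wilcoxon-Mann-Whitney with midranks, conditional on the class totals; EGDs missing at random;
- ESG intact/partial/open: 50/30/20%;
- HAPC: 75/15/10%, 85/10/5% or 95/4/1%.

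For each possible table, the p-value is the conditional probability of a rank sum W at least as far from n1(N+1)/2 as the one observed. Multinomial probabilities are then summed over all tables. At 12 v 12 the type I error is 3.3% (50/30/20 in both arms) and power is 17%, 34% and 63%. 

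One missing EGD, complete-case result compared with scoring it open:

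| | HAPC 75/15/10 | 85/10/5 | 95/4/1 |
|---|---|---|---|
| Missing in HAPC arm (11 v 12): significance lost | 10.2% | 19.4% | 32.9% |
| Missing in ESG arm (12 v 11): significance gained | 5.8% | 7.0% | 4.1% |
| Average over arms | 8.0% | 13.2% | 18.5% |

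The averages are (10.2 + 5.8)/2, (19.4 + 7.0)/2 and (32.9 + 4.1)/2; changes in the opposite direction are below 0.1%.

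With one missing in each arm (11 v 11), scoring both open loses significance in 5%, 10% and 18% of trials; scoring HAPC open and ESG intact loses it in 11%, 22% and 37%.

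One example: ESG 6/4/2 v HAPC 11/0/0 gives W = 11 x 9 = 99 against an expected 11 x 24/2 = 132, p = 0.014. Add the twelfth HAPC patient as open (11/0/1) and p = 0.069. This is an illustration, not the typical case.

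**4. How likely a missing EGD is.** P(at least one of 24) = 1 - (1 - q)^24, which is 38%, 71% and 92% for an assumed q of 2%, 5% and 10%.

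**5. Precision at 12 per arm.** For an assumed 9/12 v 6/12 intact, the difference is 0.75 - 0.50 = +25 points. Inverting two one-sided exact score tests on a 0.005 grid gives a 95% interval of -0.155 to 0.600, about -16 to +60 points.

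**The case against.** A reader might infer that the plan names no primary analysis. It does name one, and since 8.2.1 has a single aim, the natural reading attaches the hierarchical model to durability. The defect is that the model is unspecified and unlinked.

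A reader might also infer from "Additional outcomes and analyses not specified here are considered exploratory and post-hoc and will be clearly identified as such in any publications" that any between-arm durability test must be reported as post-hoc. That does not follow: durability is a specified outcome and a primary model is mentioned, however thinly.

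On the read, it can be said that the plan does imply an answer. An added, inter-observer read sounds supportive, so the site read leads. That is probably right, but it is never stated. Nor do the documents show that the site reader knows the arm: research staff are unblinded, the medical record omits assignment, and the EGD is a clinical procedure. The case for the external read rests on its stated blinding, not on demonstrated bias in the site read.

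On size, quoting only a missing HAPC EGD would be one-sided; under missing at random the ESG arm is as likely, and the change there is small. The largest losses assume 95% intact with HAPC, where a missing EGD would truly be open only 1% of the time. Scoring as open is a stress test, and significance is a limited yardstick for a declared pilot with no stated alpha. All of this stands and sets the size of the claim.

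Finally, complete-case is a defensible lead analysis. The criticism is that the plan does not state it or reconcile it with the mITT set.

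**Conclusion.** The point holds, and should be fixed before durability data are seen.

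- The power sentence is wrong as written: the plan's own sample size section rules out the calculation that it cites. This needs no assumption. It is not evidence that the trial lacks power, since that depends on rates the documents do not give. A pilot without a power calculation is acceptable, and the plan says so openly elsewhere.
- The lead read is undesignated, and the only read stated to be blinded appears to be the supportive one.
- The durability analysis is in effect complete-case unless other data are modelled jointly, and this is not reconciled with the mITT definition. One missing EGD scored open changes significance in about 8%, 13% and 18.5% of trials averaged over arms, under the assumed rates and test. That is enough to justify a rule; it does not show that a single missing EGD usually settles the result.
- The ANCOVA covariate reference is empty. This and the %TBWL label are minor wording faults.

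**What to change.** 1. *Replacement of withdrawn subjects*: delete the power sentence. State that 12 per arm is a pilot size with no power calculation, and give illustrative precision (an assumed 9/12 v 6/12 intact is +25 points, exact 95% CI about -16 to +60).
2. *Trial Intervention* and 8.2.1: make the planned external blinded rating the lead read and the site read supportive. Name one small-sample analysis of the three ordered classes, for example an exact Wilcoxon-Mann-Whitney test. Report the difference in proportion intact with its exact CI as a descriptive summary, because it is a different measure from the rank comparison and the two can disagree.
3. *Missing Data*: for durability, say that the lead analysis uses treated patients with a readable week-26 EGD and that this departs from the full mITT set. Report missing EGDs by arm with reasons. Add two bounding sensitivity analyses: all missing scored open; and missing HAPC scored open with missing ESG scored intact.
4. Section 8.2.2: adjust each change or score outcome for its own baseline value, and %TBWL and %EWL for pre-operative weight.
5. *Power and Sample Size*: call %TBWL secondary, as elsewhere.

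Cost: text only. The external read and baseline values are already planned, so there are no new visits, tests or patients. The sponsor gives up the power assurance and changes the apparent role of the site read.

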Twenty-four eligible participants will be block-randomized 1 to 1 treatment (12 participants) and control (12 participants) groups. All participants will undergo endoscopy and those without endoscopic contraindications will be eligible. All treatment group subjects will undergo combined HAPC and ESG where APC is applied according to on-label use prior to the standard ESG technique for enhanced fibrosis along the site of the plications potentially providing an avenue for longer and more durable ESG while minimizing the associated complications. Control subjects will undergo traditional ESG alone. All participants will undergo a repeat upper endoscopy at 26 weeks (6 months) +/- 2 weeks to evaluate the durability of the endoscopic sutures. All subjects will undergo research MRI at baseline and 26 weeks +/- 2 weeks to evaluate and grade the durability of the created gastroplasty, gastric motility, and gastric accommodation. This specially developed MRI protocol at Mayo offers a gold standard in evaluating gastroplasty durability. Additionally, at both baseline and 26 weeks +/- 2 weeks, all patients will undergo gastric scintigraphy to evaluate and measure gastric emptying.

Endpoints Effectiveness

Primary:

- Assess durability of endoscopic plications and sutures 26 weeks (6 months) +/- 2 weeks post procedure between patients receiving HAPC/ ESG vs traditional ESG alone.

Secondary:

- %TBWL in the combined HAPC and ESG group compared to traditional ESG at 6 and 12 months.
- Assess the procedure safety.
- % Excess weight loss (EWL) at 6 and 12 months between both groups.
- Proportion with $\geq 25\%$ EWL at 6 and 12 months by randomized arm.
- % of patients in the combined HAPC and ESG group achieving $\geq 5\%$ TBWL at 6 and 12 months compared to ESG alone.
- % of patients in the combined HAPC and ESG group achieving $\geq 10\%$ TBWL at 6 and 12 months compared to ESG alone.
- Changes in quality of life assessed using standard validated questionnaires (IWQOL-lite and SF-36) at 6 and 12 months compared to baseline.
- Changes in depression assessed using PHQ-9 questionnaire at 6 and 12 months compared to baseline.

- Improvement/reduction of hunger and desire to eat evaluated using validated self-reported ratings of appetite based on a 100-mm visual-analogue scale at 6 and 12 months compared to baseline.
- Improvement in eating behaviors evaluated using the Three Factor Eating Questionnaire (TFEQ) at 6 and 12 months compared to baseline.

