- Improvement in obesity related comorbidities (blood pressure, fasting glucose, HbA1c, lipid panel, liver enzymes) at 6 and 12 months compared to baseline.
- Changes in gastric motility, volume, accommodation, and constructed gastroplasty on MRI at 6 months compared to baseline.
- Changes in gastric emptying evaluated by gastric emptying study at 6 months compared to baseline.
- Changes in liver biochemical panel, and glucose homeostasis parameters at 6 months compared to baseline between the two groups.

Safety

- The incidence, frequency, and severity of adverse events related to treatment with the device will be reported throughout the duration of the study.
- Goal is <5% rate of serious adverse events related to the device or procedure (as determined by the site PI). Serious adverse events will be classified in the Adverse Events table.

Study Setting

The study will be conducted at 1 US center, Mayo Clinic in Rochester, MN. The maximum enrollment will be limited to 24 participants. The expected enrollment period is 6 months.

Subjects

Participants will be adult patients (Ages 21 \geq and \leq 65) with a BMI \geq 30 and \leq 40 kg/m² that meet the eligibility criteria below. All eligibility criteria must be met at the time of randomization.

Inclusion Criteria

1. Age 21-65
2. BMI \geq 30 and \leq 40 kg/m²
3. Willingness to comply with the substantial lifelong dietary restrictions required by the procedure.
4. History of failure with non-surgical weight-loss methods.
5. Willingness to follow protocol requirements, including signed informed consent, routine follow-up schedule, completing laboratory tests, and completing diet counseling.

6. Residing within a reasonable distance from the investigator's office and able to travel to the investigator to complete all routine follow-up visits.
7. Ability to give informed consent.
8. Women of childbearing potential (i.e., not post-menopausal or surgically sterilized) must agree to use adequate birth control methods.

Exclusion Criteria

1. History of foregut or gastrointestinal (GI) surgery (except uncomplicated cholecystectomy or appendectomy).
2. Prior gastrointestinal surgery with sequelae, i.e. obstruction, and/or adhesive peritonitis or known abdominal adhesions.
3. Prior open or laparoscopic bariatric surgery.
4. Prior surgery of any kind on the esophagus, stomach, or any type of hiatal hernia surgery.

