The primary endpoint for power and sample size is durability of plications on repeat endoscopy 6 months after initial procedure with HAPC and ESG and ESG alone. Another primary endpoint for power and sample size is %TBWL at 6 and 12 months.

We plan a 1:1 randomization scheme that allocates to either HAPC ESG (12 patients) or ESG alone (12 patients). Given the pilot nature of this trial, no formal power calculation is feasible or warranted.

Statistical Analysis

Statistical analyses of randomized groups at 6 and 12 months will be performed based on a modified intent-to-treat (mITT) principle for efficacy analyses. Patients randomized but subsequently withdrawn or identified as meeting exclusion criteria prior to intervention (as applied to both the treatment and control arms) will be excluded from the analysis if the reason for exclusion is documented and unrelated to the randomized arm.

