8.2.2 Secondary Aims

Continuous secondary outcomes, including %TBWL^b, %EWL^c, change in systolic and diastolic blood pressure and change in HbA1c, QOL questionnaires such as the SF-36, IWQOL, PHQ-9, and eating behavior scores will be compared between treatment arms using ANCOVA with adjustment for the same variables specified in the primary analysis.

Binary outcomes, including proportion with $\geq 25\%$ reduction in %EWL and incidence of esophagitis will be compared between treatment arms by Pearson Chi-square test.

Among all subjects, %EWL will be compared at 6 and 12 months between both arms of the study.

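### The randomisation is called stratified in one section and described without strata in another; no factor is named, so any prognostic stratum would go unaccounted for in the analyses as written

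*Combined protocol and SAP*

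**What the plan says.** Three places describe the allocation.

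- Study Design, General Description: "Twenty-four eligible participants will be block-randomized 1 to 1 treatment (12 participants) and control (12 participants) groups". Power and Sample Size repeats the 12 and 12.
- Trial Procedures, Randomization: "1:1 allocation per a computer-generated randomization using variable block randomization". Strata are not mentioned.
- Statistical Analysis, Randomization and Data Collection: "Stratified block randomization schedules will be uploaded to REDCap".

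No section names a stratification factor, a number of strata or a block size. Site cannot be the implied stratum, because Study Setting says "The study will be conducted at 1 US center, Mayo Clinic in Rochester, MN".

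The analysis text does not settle the matter. Section 8.2.2 says that binary outcomes "will be compared between treatment arms by Pearson Chi-square test". For continuous secondary outcomes it plans ANCOVA and takes the covariates from the primary analysis, but section 8.2.1 names only the outcome and gives no covariates. The Missing Data section calls the primary model a hierarchical regression and lists no terms.

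**The concern.** A statistician could not build one allocation list from these sentences, and a reader of the results could not tell which list was used. The analysis should match the allocation. Stratified blocks balance the arms on the factor, which makes the estimated difference less variable. An analysis that omits the factor leaves its variance in the residual and so reports a standard error that is too large. In a trial of 24 patients, that gives up precision that costs almost nothing to keep.

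A related question arises for %EWL whether or not the list is stratified. Its denominator depends on baseline BMI, so BMI drives part of its variance by construction, and the plan names no baseline covariate for it.

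**Working it through.** **Figures in the plan.** There is no power, standard error or alpha to reproduce, because Power and Sample Size declines a formal calculation. The only stated figure is 24/2 = 12 per arm.

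**1. Cost of ignoring a stratum.** Inputs: 12 per arm (plan); two balanced strata, total SD of 1, two-sided 5% and stratum R² of 0.10, 0.20 or 0.30 (all assumed).

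- Reported SE when the stratum is ignored: about √(2/12) = 0.408 SD.
- True SE: √[(1 − R²) × 2/12] = 0.387, 0.365 and 0.342 SD.
- Ratio: 1/√(1 − R²) = 1.054, 1.118 and 1.195, an overstatement of about 5%, 12% and 20%.
- Actual size by the normal approximation, P(|Z| > 1.96 × ratio): 3.9%, 2.8% and 1.9%. Simulation of the t-test gives 3.8%, 2.8% and 1.9%.
- In simulation, putting the factor in the model restores 5% and raises power for an assumed 1.2 SD difference from 81%, 82% and 83% to 84%, 88% and 92%.

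A separate simulation, with random stratum sizes and blocks of 4 and 6 (assumed), agrees. At R² of 0, 0.10 and 0.25 the ratio of reported to true SE was 0.99, 1.04 and 1.14, and the size was 5.0%, 4.0% and 2.2%.

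**2. Binary outcomes.** Simulation with two strata, 6 per arm per stratum and assumed response rates gave:

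| | Pearson | Stratified exact |
|---|---|---|
| Type I error | 3.4–6.5% | 1.7–2.4% |
| Power, 30% vs 80% | 77% | 61% |
| Power, 15%/55% vs 65%/95% by stratum | 69% | 55% |

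A stratified exact test would therefore add conservatism. A Cochran-Mantel-Haenszel test was no worse than Pearson in the same kind of simulation, provided no continuity correction is applied.

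**3. BMI and %EWL.** With ideal weight set at BMI 25 (the plan's footnote), %EWL = %TBWL × f, where f = BMI/(BMI − 25). A 16% loss is 16 × 30/5 = 96% EWL at BMI 30 and 16 × 40/15 = 42.7% at BMI 40. Assume BMI uniform on 30–40 and, independently of it, %TBWL with mean 16 and SD 7.

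- Mean of f = 1 + 2.5 ln 3 = 3.747. Variance of f = 62.5 × (1/5 − 1/15) − (2.5 ln 3)² = 0.790.
- Variance of %EWL = (16² + 7²) × (0.790 + 3.747²) − (16 × 3.747)² ≈ 929.
- Part due to BMI = 16² × 0.790 = 202, and 202/929 = 21.8%.
- Covariance of f with BMI = 25 × (1 − ln 3) = −2.465. Squared correlation = 2.465²/(8.333 × 0.790) = 0.923. A linear BMI term thus explains 0.923 × 21.8% ≈ 20%.
- Two classes split at BMI 35 have mean f of 1 + 5 ln 2 = 4.466 and 1 + 5 ln 1.5 = 3.027. They explain 16² × (1.439/2)²/929 ≈ 14%.

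Under the same assumptions BMI explains none of the variance of %TBWL.

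**4. Arm sizes.** For arms of a and b, the SE relative to 12:12 is √(1/a + 1/b)/√(2/12): 1.003 at 13:11 and 1.014 at 14:10. With assumed block sizes of 2/4, 4/6 or 2/4/6 drawn at random, a single list misses 12:12 among the first 24 in 11–23% of simulated schedules. With two strata the figure is 35–44%, over those block sizes and fixed blocks of 4 or 6. A single list of fixed blocks of 4 or 6, or of variable blocks chosen to total 24, never misses.

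**The case against.** The strongest reply is that this is one missing sentence in a pilot. Several stronger inferences that a reader might draw do fail.

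- **That the two descriptions are mutually exclusive.** They are not. The Randomization section is silent on strata rather than opposed to them, and variable blocks can be run within strata. The description is incomplete and unreconciled.
- **That neither scheme can deliver 12:12.** A single list whose blocks total 24 does so for the first 24 randomised. The plan does not say how its list was built, and a slight imbalance costs very little.
- **That error bars would differ from those stated.** The plan states none.
- **That false positives are at risk.** The error runs the other way.
- **That no analysis will use strata.** Only the chi-square is unstratified as written. The ANCOVA and hierarchical-model covariates are undefined, so adjustment is unspecified, not ruled out.

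It is also fair that the loss requires a stratum that exists, is prognostic and is ignored, and the documents establish none of these. The BMI argument is an algebraic feature of %EWL and says nothing about suture durability, the primary endpoint.

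What stands is that two current sections give different accounts of the allocation, no factor is named, and no written analysis would carry a stratum if there is one.

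**Conclusion.** The point holds as a conditional one and should be corrected; it does not threaten validity. If the list is stratified by a prognostic factor and the analysis omits it, standard errors are overstated by about 5%, 12% and 20% at an assumed R² of 0.10, 0.20 and 0.30, with no effect at 0. The R² values and the two-stratum layout are assumptions. Separately, continuous screening BMI would explain about 20% of %EWL variance under the assumed BMI and weight-loss distributions, and none of %TBWL variance by construction. Arm-size drift is a minor matter of wording: besides block overrun, the rule under Replacement of withdrawn subjects randomises new patients until 24 are treated and has no provision by arm.

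**What to change.** 1. Make the General Description, Randomization, and Randomization and Data Collection sections give one account that matches the list actually generated. Keep block sizes in a document withheld from recruiting staff.
2. If the list is stratified, name the factor and its levels, include it in the primary and ANCOVA models, and replace the Pearson chi-square with a Cochran-Mantel-Haenszel test stratified by that factor, without continuity correction. Do not substitute a stratified exact test.
3. If the list is not stratified, delete the word Stratified from Randomization and Data Collection.
4. In either case, list screening BMI as a continuous covariate in the %EWL model.
5. Describe 12 per arm as a target.

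The cost is protocol and SAP wording plus one degree of freedom per added term (for one two-level factor, residual degrees of freedom fall from 22 to 21). In the simulation, adjustment lost nothing at R² of 0. The change should be made before outcome data are seen.
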